### 1.3. Sample Size and Power

There is no formal efficacy or safety hypothesis to be tested in this study, and therefore no formal size calculation was performed.

The rolling 6 design is implemented for the study. The first 6 subjects will be enrolled at dose level 0 in Group A. During the DLT assessment window, if 0 or 1 out of these 6 subjects experience DLTs in Group A, Group B will open and 6 subjects will be enrolled at dose level 0 in Group B. However, if 2 or more subjects experience DLTs in Group A, 6 additional subjects will be enrolled at dose level -1 in Group A and Group B will not open. Subjects who discontinue early for a non-DLT defined reason during the DLT assessment window will not be evaluable for DLT and may be replaced. The aforementioned subjects are DLT evaluable subjects.

With consideration for subject replacement, up to 24 subjects will be enrolled to the study.

## **2. TYPE OF PLANNED ANALYSIS**

### **2.1. Interim Analysis**

No formal interim analyses are planned in this Phase 1b study.

### **2.2. Final Analysis**

Final study reporting is expected to occur after all subjects have discontinued from the study.

### **3. GENERAL CONSIDERATIONS FOR DATA ANALYSES**

As the study was terminated early with only 9 subjects enrolled, the synoptic CSR will only include listings for efficacy analyses. Both summarized tables and listings will be provided for safety analyses.

#### **3.1. Analysis Sets**

Analysis sets define the subjects to be included in an analysis. The analysis set will be identified and included as a subtitle of each table, figure, and listing.

##### **3.1.1. Full Analysis Set**

Full Analysis Set (FAS) includes all subjects who took at least 1 dose of study drug (ENTO).

This analysis set will be used in the analyses of subject characteristics, drug exposure, safety, and efficacy.

##### **3.1.2. Dose-Limiting Toxicity (DLT) Analysis Set**

DLT Analysis Set includes all subjects in the FAS who meet at least one of the following criteria:

- Receive at least 21 days of ENTO during the DLT assessment window (refer to Section 1.2).
- Experience a DLT during the DLT assessment window.

This analysis set will be used for analyses related to DLT.

##### **3.1.3. Pharmacokinetic Analysis Sets**

The Pharmacokinetic (PK) Analysis Sets include all subjects in the FAS who have necessary baseline and at least 1 non-missing post-treatment assessments.

#### **3.2. Subject Grouping**

Due to the early termination of the study, only one dose is evaluated. Subjects will be presented under '400 mg BID' dose level for FAS, DLT Analysis Set, and PK Analysis Sets.

#### **3.3. Strata and Covariates**

Not applicable.

#### **3.4. Examination of Subject Subgroups**

Not applicable.

### **3.5. Multiple Comparisons**

Not applicable.

### **3.6. Missing Data and Outliers**

#### **3.6.1. Missing Data**

In general, missing data will not be imputed unless methods for handling missing data are specified. Exceptions are presented in this document.

The handling of missing or incomplete date for AE onset is described in Section 7.1.5.2, and for prior medication and concomitant medication in Section 7.4.

#### **3.6.2. Outliers**

Outliers will be identified during the data management and data analysis process, but no sensitivity analyses will be conducted. All data will be included in the data analysis.

### **3.7. Data Handling Conventions and Transformations**

In general, age (in years) on the first dosing date of study drug will be used for analyses and presentation in listings. For enrolled subjects who are not dosed with any study drug, the enrollment date will be used instead of the first dosing date of study drug. For screen failures, the date the informed consent was signed will be used for age calculation. If only the birth year is collected on the CRF, “01 July” will be used for the unknown birth day and month for the purpose of age calculation. If only birth year and month are collected, “01” will be used for the unknown birth day.

Non-PK laboratory data that are continuous in nature but are less than the lower limit of quantitation (LOQ) or above the upper LOQ will be imputed as follows:

- A value that is 1 unit less than the LOQ will be used to calculate descriptive statistics if the datum is reported in the form of “< x” (where x is considered the LOQ). For example, if the values are reported as < 50 and < 5.0, values of 49 and 4.9, respectively, will be used to calculate summary statistics. An exception to this rule is any value reported as < 1 or < 0.1, etc. For values reported as < 1 or < 0.1, a value of 0.9 or 0.09, respectively, will be used to calculate summary statistics.
- A value that is 1 unit above the LOQ will be used to calculate descriptive statistics if the datum is reported in the form of “> x” (where x is considered the LOQ). Values with decimal points will follow the same logic as above.
- The LOQ will be used to calculate descriptive statistics if the datum is reported in the form of “≤ x” or “≥ x” (where x is considered the LOQ).

Plasma concentration values that are below the limit of quantitation (BLQ) will be presented as “BLQ” in the concentration data listing. Values that are BLQ will be treated as 0 at pre-dose time points, and one-half the value of the LOQ at post-baseline time points.

The following conventions will be used for the presentation of summary and order statistics:

- If at least 1 subject has a concentration value of BLQ for the time point, the minimum value will be displayed as “BLQ.”
- If more than 25% of the subjects have a concentration data value of BLQ for a given time point, the minimum and Q1 values will be displayed as “BLQ.”
- If more than 50% of the subjects have a concentration data value of BLQ for a given time point, the minimum, Q1, and median values will be displayed as “BLQ.”
- If more than 75% of the subjects have a concentration data value of BLQ for a given time point, the minimum, Q1, median, and Q3 values will be displayed as “BLQ.”
- If all subjects have concentration data values of BLQ for a given time point, all order statistics (minimum, Q1, median, Q3, and maximum) will be displayed as “BLQ.”

### **3.8. Analysis Visit Windows**

#### **3.8.1. Definition of Study Day**

Study day will be calculated from the first dosing date of study drug and derived as follows:

- For post-treatment study days: Assessment Date – First Dosing Date + 1
- For days prior to the first dose: Assessment Date – First Dosing Date

Therefore, Study Day 1 is the day of first dose of study drug administration.

Baseline is defined as the last non-missing record on or prior to the date of Study Day 1, unless otherwise specified.

#### **3.8.2. Analysis Windows**

The nominal visit as recorded on the CRF will be used when data are summarized by visit and no analysis window will be derived.

## **4. SUBJECT DISPOSITION**

### **4.1. Subject Enrollment and Disposition**

A summary of subject disposition will be provided by dose level based on FAS. This summary will present the number and percentage of subjects in the following categories:

- ENTO discontinuation
  - Reasons of ENTO discontinuation
- Included in the DLT analysis set
- Study discontinuation
  - Reasons of Study discontinuation

The denominator for the percentage calculation will be the total number of subjects in FAS corresponding to that column.

A data listing of subject enrollment to describe the site, subject number, date of first and last dose and dose level of ENTO, analysis set inclusion (FAS and DLT analysis sets), reasons for ENTO discontinuation, and reasons for study discontinuation will be provided.

### **4.2. Extent of Study Drug Exposure and Adherence**

Extent of exposure to study drug will be examined by assessing the total duration of exposure to study drug and the level of adherence to the study drug specified in the protocol. The summaries will be based on FAS.

#### **4.2.1. Exposure to Study Drug**

Total duration of exposure to study drug will be defined as last dosing date minus first dosing date plus 1, regardless of any temporary interruptions in study drug administration, and will be expressed in weeks using up to 1 decimal place (eg, 4.5 weeks).

The total duration of exposure to ENTO will be summarized using descriptive statistics and using the number and percentage of subjects exposed for at least 1 day, 14 days, 28 days, and 2, 3, 6, 9 months, etc.

The number of cycles subjects were exposed to study drug will be summarized using descriptive statistics, as well as the number and percentage of subjects exposed to a given cycle category (eg, Cycle X).

The number and percentage of subjects, who had dose reduction or interruption, and the reason, will also be summarized.

#### **4.2.2. Adherence to Study Drug**

A by-subject listing of study drug accountability (dispenses and returns) and dose modification will be provided by subject ID number (in ascending order) and visit (in chronological order).

#### **4.3. Protocol Deviations**

Subjects who did not meet the eligibility criteria for study entry, but enrolled in the study will be identified regardless of whether they were exempted by the sponsor or not. A by-subject listing will be provided for those subjects who did not meet at least 1 eligibility (inclusion or exclusion) criterion. The listing will present the eligibility criterion (or criteria if more than 1 deviation) that subjects did not meet and related comments, if collected.

Protocol deviations occurring after subjects entered the study are documented during routine monitoring. A by-subject listing will be provided for those subjects with important protocol deviation.

## **5. BASELINE CHARACTERISTICS**

The baseline characteristics will be presented by treatment group based on FAS.

### **5.1. Demographics**

Subject demographic variables (ie, age, sex, race, and ethnicity) will be summarized using descriptive statistics for age, and using number and percentage of subjects for sex, race, and ethnicity.

Age will be calculated by the formula:

$$\text{Age (in years)} = (\text{date of first dose} - \text{date of birth} + 1) / 365.25 \text{ (round down to an integer)}$$

A by-subject demographic listing, including the informed consent date, will be provided by subject ID number in ascending order.

### **5.2. Other Baseline Characteristics**

Other baseline characteristics include body weight (in kg), height (in cm), body mass index (BMI; in kg/m^2), ECOG status, cytogenetics, genetic risk group classification, and type of hematologic malignancy. BMI will be calculated by the formula:

$$\text{BMI (kg/m}^2\text{)} = \text{weight} / (\text{height}^2) \text{ (round to 1 decimal point).}$$

Other baseline characteristics will be summarized using descriptive statistics.

A by-subject listing of other baseline characteristics will be provided by subject ID number in ascending order.

### **5.3. Medical History**

Medical history will be collected at screening for disease-specific and general conditions (ie, conditions not specific to the disease being studied). General medical history data will not be coded.

A by-subject listing of disease-specific (including hematologic malignancy type, date of initial diagnosis, and detailed diagnosis) and general medical history will be provided by subject ID number in ascending order.

### **5.4. Prior Anti-Cancer Therapy**

A by-subject listing of prior anti-cancer therapy and prior radiation therapy will be provided by subject ID number in ascending order.

## **6. EFFICACY ANALYSES**

Assessment of clinical response in subjects with hematologic malignancies other than AML will be according to the latest set of published response criteria. Assessment of clinical response in subjects with AML will be according to the modified International Working Group criteria and will include findings on examination of blood, bone marrow and physical examination.

Clinical response will be evaluated by investigator assessments. All efficacy endpoints will be analyzed by treatment group using FAS.

### **6.1. Primary Efficacy Endpoints**

Not applicable.

### **6.2. Secondary Efficacy Endpoints**

Not applicable.

### **6.3. Exploratory Efficacy Endpoints**

#### **6.3.1. Definition of Exploratory Efficacy Endpoints**

**6.3.2. Analysis Methods of Exploratory Efficacy Endpoints**

CCI [Redacted]

[Redacted]

[Redacted]

[Redacted]

[Redacted]

**6.3.3. Changes from Protocol-Specified Efficacy Analyses**

CCI [Redacted]

## **7. SAFETY ANALYSES**

Safety analyses are conducted using FAS, unless otherwise specified.

### **7.1. Adverse Events and Deaths**

#### **7.1.1. Adverse Event Dictionary**

Clinical and laboratory adverse events (AEs) will be coded using the current version (ie, Version 21.0) of Medical Dictionary for Regulatory Activities (MedDRA). System organ class (SOC), high-level group term (HLGT), high-level term (HLT), preferred term (PT), and lower-level term (LLT) will be provided in the AE dataset.

#### **7.1.2. Adverse Event Severity**

Adverse events are graded by the investigator as Grade 1, 2, 3, 4, or 5 according to toxicity criteria specified in the Common Toxicity Criteria for Adverse Events (CTCAE) Version 4.03 {[U.S. Department of Health and Human Services 2010](#)}. The severity grade of events for which the investigator did not record severity will be categorized as “missing” for tabular summaries and data listings and the missing category will be listed last in data presentation.

#### **7.1.3. Relationship of Adverse Events to Study Drug**

Related AEs are those for which the investigator selected “Related” on the AE CRF to the question of “Related to Study Treatment Entospletinib”. Relatedness will always default to the investigator’s choice, not that of the medical monitor. Events for which the investigator did not record relationships to study drug will be considered related to study drug for summary purposes. However, by-subject data listings will show the relationship as missing.

#### **7.1.4. Serious Adverse Events**

Serious adverse events (SAEs) will be identified and captured as SAEs if the AEs met the definitions of SAEs that were specified in the study protocol. SAEs captured and stored in the clinical database will be reconciled with the SAE database from then Gilead Drug Safety and Public Health Department before data finalization.

#### **7.1.5. Treatment-Emergent Adverse Events**

##### **7.1.5.1. Definition of Treatment-Emergent Adverse Events**

Treatment-emergent adverse events (TEAEs) are defined as 1 or both of the following:

- Any AEs with an onset date on or after the study drug start date and no later than 30 days after permanent discontinuation of study drug
- Any AEs leading to premature discontinuation of study drug

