### **3.5. Discontinuation Criteria**

#### **3.5.1. Discontinuation of Study Treatment**

Study treatment may be discontinued in the following instances:

- Intercurrent illness that would, in the judgment of the investigator, affect assessments of clinical status to a significant degree. Following resolution of intercurrent illness, the subject may resume study dosing at the discretion of the investigator.
- Unacceptable toxicity, or toxicity that, in the judgment of the investigator, compromises the ability to continue study-specific procedures or is considered to not be in the subject's best interest
- Group A: If there is disease progression or if there has not been an improvement in cytopenias, blast count, peripheral blood or marrow that would suggest clinical benefit, the subject should be removed from study treatment per Investigator discretion. Decisions regarding continuation of ENTO monotherapy in subjects should be determined by the Investigator.
- Group A: Requires continued treatment with hydroxyurea after Cycle 1
- Group B: If a CR or CRi is not achieved by the end of induction Cycle 2, the subject will be considered to have refractory leukemia, to meet the definition of treatment failure and study endpoint criteria, and will be discontinued from the study treatment

- Subjects may be removed in the case of new CNS disease or other new sites of extramedullary involvement
- Subject request to discontinue for any reason. Subjects who withdraw from the study treatment phase of the study should still be followed for survival until 3 years from the last study visit (see Section 6.8.3, Long term follow up)
- Subjects with noncompliance to study treatment administration, study procedures, or study requirements that increase risk or substantially compromise the interpretation of study results should be withdrawn from study treatment.
- Pregnancy or breastfeeding begins during the study
- The investigator, in consultation with the Gilead Sciences Medical Monitor or designee, may withdraw any subject from the study treatment, if, in the investigator's opinion, it is not in the subject's best interest to continue.
- Initiation of non-study specific anti-cancer therapy
- Discontinuation of the study treatment at the request of Gilead, a regulatory agency or an institutional review board or independent ethics committee (IRB/IEC)

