### **3.6. End of Treatment**

Subjects will be removed from study treatment when any of the criteria listed in Section 3.5.1 apply. The End of Treatment (EOT) visit should be completed when a subject discontinues study treatment and prior to initiating a new therapy.

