### **6.8.2. 30-day Follow-up**

Subjects will be contacted by telephone 30 days ( $\pm$  7 days) after the last dose of ENTO to assess AEs and review concomitant medications. The 30-day follow-up visit may be substituted by a scheduled study visit if it occurs within the same window.

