### **6.8.3. Long Term Follow-up**

Long term follow-up (LTFU) for OS begins after EOT or the last study visit if EOT does not occur. Subjects will be contacted by telephone or during a routine clinic visit every 6 months ( $\pm$  4 weeks) to gather leukemia treatments, other malignancies, and survival for up to 3 years after EOT or the last study visit. Every attempt should be made to keep the subject in LTFU for OS.

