#### Adverse Events

Following initiation of study medication, collect all AEs, regardless of cause or relationship, until 30 days after last administration of study IMP must be reported to the eCRF database as instructed.

All AEs should be followed up until resolution or until the AE is stable, if possible. Gilead Sciences may request that certain AEs be followed beyond the protocol defined follow up period.

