### **8.6.2. Adverse Events**

All AEs will be listed. The AE summarization will focus on treatment-emergent AEs. Treatment-emergent AEs are defined as AEs that onset in the period from the first dose of study treatment to 30 days after the permanent discontinuation of study treatment or that lead to permanent study treatment discontinuation.

AEs that occur before the first dose of study treatment or >30 days after study treatment discontinuation will be included in data listings.

AEs will be classified using Medical Dictionary for Regulatory Activities (MedDRA) with descriptions by System Organ Class, High-Level Group Term, High Level Term, Preferred Term, and Lower-Level Term. The severity of AEs will be graded by the investigator according to the CTCAE, Version 4.03 (<http://www.hrc.govt.nz/sites/default/files/CTCAE%20manual%20-%20DMCC.pdf>), whenever possible. If a CTCAE criterion does not exist for a specific type of AE, the grade corresponding to the appropriate adjective will be used by the investigator to describe the maximum intensity of the AE: Grade 1 (mild), Grade 2 (moderate), Grade 3 (severe), Grade 4 (life threatening), or Grade 5 (fatal). The relationship of the AE to study treatment will be categorized as related or unrelated.

Treatment-emergent AEs will be summarized by presenting the number and percentage of subjects with treatment-emergent AEs by severity grade. Subjects who report multiple treatment-emergent AEs under the same Preferred Term (or System Organ Class) are counted only once under the worst severity grade. The summary will be presented in decreasing frequency of System Organ Class and Preferred Term of the 'Total' column. Within the same frequency, the AEs are ordered in the alphabetical order of System Organ Class and Preferred Term. Separate listings and summaries will be provided for the following types of treatment-emergent AEs:

- Study treatment related AEs
- AEs with severity  $\geq$  Grade 3
- AEs leading to study treatment interruption and/or dose modification
- AEs leading to study treatment discontinuation
- Study treatment related SAEs
- DLT
- DLT rates and their 90% CI

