#### **7.2.1.1. Treatment-Emergent Laboratory Abnormalities**

Treatment-emergent laboratory abnormalities are defined as values that increase at least 1 toxicity grade from baseline at any post-baseline time point, up to and including the date of last dose of study drug plus 30 days for subjects who permanently discontinued study drug, or the last available date in the database snapshot for subjects who were still on treatment at the time of an interim analysis. If the relevant baseline laboratory value is missing, any abnormality of at least Grade 1 observed within the time frame specified above will be considered to be treatment emergent.

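### The all-causality TEAE tables run to 30 days after the last ENTO dose with no flag or supplementary cut at the next anti-cancer therapy, and no visible SAP output shows that therapy or its start date

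*SAP*

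**What the plan says.** **Adverse events.** SAP 7.1.5.1 sets the upper limit for onset at "no later than 30 days after permanent discontinuation of study drug". Events that lead to premature discontinuation also count. Protocol 8.6.2 matches, running from first dose "to 30 days after the permanent discontinuation of study treatment or that lead to permanent study treatment discontinuation". Protocol 7.3 tells sites to "collect all AEs, regardless of cause or relationship, until 30 days after last administration of study IMP".

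**Laboratory abnormalities.** SAP 7.2.1.1 uses the same end point: "up to and including the date of last dose of study drug plus 30 days for subjects who permanently discontinued study drug".

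**New therapy.** Protocol 3.5.1 lists "Initiation of non-study specific anti-cancer therapy" among the reasons for stopping study treatment. Protocol 3.6 adds: "The End of Treatment (EOT) visit should be completed when a subject discontinues study treatment and prior to initiating a new therapy". The safety contact in Protocol 6.8.2 is a telephone call 30 days (± 7 days) "after the last dose of ENTO to assess AEs and review concomitant medications". Long-term contacts under Protocol 6.8.3 take place every 6 months "to gather leukemia treatments, other malignancies, and survival for up to 3 years after EOT".

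**Outputs.** SAP 7.1.6 plans TEAE tables for all causes and, separately, for ENTO-related events. Its full AE listing is marked only for treatment-emergent status. SAP 5.4 lists prior anti-cancer therapy. SAP 7.4 lists prior and concomitant medications. The Statistical Methods part of the protocol synopsis says that therapies given after the study will be summarized on the FAS. No matching output appears in the visible SAP, and SAP 7.7 reports no departure from the protocol's safety analyses.

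**The concern.** The EOT visit is placed before new therapy and the AE contact comes 30 days after the last dose, so the plan leaves room for another regimen to start between the two. An infection, cytopenia or death under that regimen meets the TEAE definition. It then enters the all-causality, Grade 3 or higher, serious and fatal tables beside events that occurred on ENTO.

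The study has one dose column and no control arm, so nothing in those tables lets a reader discount toxicity from a later treatment. The listings do not help either. They show when ENTO stopped and when an event began, but not whether something else had started in between. At stake is how clearly the tolerability tables describe ENTO monotherapy in a very small group.

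**Working it through.** This is a question of definition. The plan gives no figure to reproduce, and SAP 1.3 states that no hypothesis is tested and no formal sample size calculation was made. The check is textual, with arithmetic for scale only.

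**1. Is there a cut or flag?** SAP 7.1.5.1, Protocol 8.6.2 and Protocol 7.3 all run to 30 days. None refers to subsequent therapy. The only marker on the AE listing in SAP 7.1.6 is treatment-emergent status.

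**2. Would the next regimen appear anywhere?** Take a drug with a complete start date after the last ENTO dose.
- Prior (SAP 7.4.1): no, because it did not start before the first dose.
- Concomitant (SAP 7.4.2): no, because drugs started after the last dose are excluded.
- Prior anti-cancer therapy (SAP 5.4): no.

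It falls outside every visible listing. A drug started on or before the last ENTO dose would appear as concomitant. The redacted parts of SAP 6.3 are not counted as missing.

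**3. Which outputs are exposed?**
- All-causality TEAE tables (all, Grade 3 or higher, serious, leading to death): exposed. Counting is by maximum severity, so a severe event after new therapy can also displace a milder event of the same term that occurred on ENTO.
- ENTO-related tables: little exposed. SAP 7.1.3 follows the investigator's attribution. Only a wrong or missing attribution lets such an event in, since a missing one is counted as related.
- DLT: little exposed. The window is Cycle 1 Days 1 to 28. A subject without a DLT needs 21 days of ENTO to be evaluable, so at most about 28 − 21 = 7 days could overlap. Non-hematologic DLTs must also be attributable to ENTO.
- Laboratory tables: minimal exposure. EOT samples come before new therapy, the 30-day contact is by telephone, and Protocol Appendix 2 schedules no laboratory test there. What remains is hematology at remission or relapse and unscheduled central samples.

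**4. Size per subject.** SAP 3 gives 9 enrolled. Assume all 9 were dosed, so that FAS = 9.
- One subject = 1/9 = 11.1% (exact 95% CI 0.3 to 48.2).
- Example: a row at 3/9 = 33.3% (7.5 to 70.1) becomes 2/9 = 22.2% (2.8 to 60.0) if one subject's only event in that row began after new therapy.

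**5. Possible overlap in time.** If new therapy starts *s* days after the last dose, the overlap is 30 − *s* + 1 days: 30, 24 and 17 days for *s* = 1, 7 and 14. The post-dose share of the window after *d* days on ENTO is 30/(*d* + 30):
- *d* = 28: 30/58 = 51.7%
- *d* = 56: 30/86 = 34.9%
- *d* = 168: 30/198 = 15.2%

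These are upper limits on calendar time, reached only if new therapy starts the day after the last dose. They are not shares of events.

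**6. Chance that at least one subject is affected.** If each of 9 subjects independently had probability *q* of an event after new therapy inside the window, the chance is 1 − (1 − *q*)^9: 61% for *q* = 0.10, 87% for 0.20 and 96% for 0.30. These values of *q* are assumptions. The documents give none, and *q* could be zero.

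**The case against.** A reader might infer that the plan reports the toxicity of the next treatment as ENTO toxicity. The documents do not support that. Treatment-emergent is a timing label, Protocol 7.1.1 says an AE need not be causally related, and SAP 7.1.6 tabulates ENTO-related events separately. An event judged unrelated stays out of those tables.

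A reader might also infer that new therapy straight after EOT is the usual course, so that about half of the window is contaminated. No document says how many subjects stopped for progression or were treated again. Group A admits only subjects who cannot receive standard of care, which weakens that presumption. The 51.7% is a constructed case.

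Other points for the plan also stand. The SAP window agrees with the protocol, so there is no conflict to resolve. Making a truncated window the main table would remove delayed ENTO effects from it, which is a debatable trade in a safety study. With 9 subjects and listings of all AEs, SAEs, deaths and dosing dates, a reader can pick out every event after the last dose. What the reader still cannot see is whether another regimen had begun by then. That gap survives the objections.

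**Conclusion.** The concern holds as a reporting gap of modest weight. Events that begin after a new regimen can enter the all-causality TEAE tables, and nothing in the visible SAP lets a reader separate them. The therapy itself is not shown, although the synopsis says it will be summarized.

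The effect is 11.1 percentage points in a row for each subject whose only event in that row began after new therapy, assuming FAS = 9. A subject who already had an event in that row changes the count only where severity is tabulated. The total effect may be nil, because the number of subjects who started new therapy within 30 days is not stated. Contamination is possible, not shown. It does not reach the DLT endpoint or the ENTO-related tables to any important degree, and it barely reaches the laboratory tables.

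**What to change.** Keep the protocol's 30-day window as the main TEAE analysis. In SAP 7.1.6:

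1. Add a by-subject listing of subsequent anti-cancer therapy with start dates. This would also supply information that the synopsis promises.
2. Flag AEs, SAEs and deaths with onset on or after the first such date.
3. Add a supplementary TEAE summary whose window ends at the earlier of last dose + 30 days or the day before new therapy.

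The cost is one listing, one flag and one table for 9 subjects. It depends on start dates being captured in the 30-day medication review or in follow-up. The protocol plans to collect these treatments but does not say that start dates are recorded, so this should be checked against the eCRF. A delayed ENTO effect that appears after new therapy drops out of the supplementary table only. It stays in the main table and the flagged listings.
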